12.3.6 Overall Best Response Assessment

Each patient will be classified according to his “best response” for the purposes of analysis of treatment effect. Best response is determined as outlined in [Section 12.7](#) from a sequence of overall response assessments.

12.4 Response Criteria for Neuroblastoma Patients with MIBG Positive Lesions**12.4.1 MIBG Positive Lesions**

Patients who have a positive MIBG scan at the start of therapy will be evaluable for MIBG response. The use of ^{123}I for MIBG imaging is recommended for all scans. If the patient has only one MIBG positive lesion and that lesion was radiated, a biopsy must be done at least 28 days after radiation was completed and must show viable neuroblastoma.

12.4.2 The following criteria will be used to report MIBG response by the treating institution:

Complete response: Complete resolution of all MIBG positive lesions
Partial Response: Resolution of at least one MIBG positive lesion, with persistence of other MIBG positive lesions
Stable disease: No change in MIBG scan in number of positive lesions
Progressive disease: Development of new MIBG positive lesions

[figure not shown]
12.4.3 The response of MIBG lesions will be assessed on central review using the Curie scale¹⁴ as outlined below. Central review responses will be used to assess efficacy for study endpoint. See [Section 8.3.2](#) for details on transferring images to the Imaging Research Center.

NOTE: This scoring should also be done by the treating institution for end of course response assessments.

The body is divided into 9 anatomic sectors for osteomedullary lesions, with a 10th general sector allocated for any extra-osseous lesion visible on MIBG scan. In each region, the lesions are scored as follows. The **absolute extension score** is graded as:

0 = no site per segment,
1 = 1 site per segment,
2 = more than one site per segment,
3 = massive involvement (>50% of the segment).

The **absolute score** is obtained by adding the score of all the segments. See diagram of sectors below:

The **relative score** is calculated by dividing the absolute score at each time point by the corresponding pre-treatment absolute score. The relative score of each patient is calculated at each response assessment compared to baseline and classified as below:

1. **Complete response:** all areas of uptake on MIBG scan completely resolved. If morphological evidence of tumor cells in bone marrow biopsy or

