THIS PROTOCOL IS FOR RESEARCH PURPOSES ONLY, SEE PAGE 1 FOR USAGE POLICY

aspiration is present at enrollment, no tumor cells can be detected by routine morphology on two subsequent bilateral bone marrow aspirates and biopsies done at least 21 days apart to be considered a **Complete Response**.

2. **Partial response:** Relative score ≤ 0.2 (lesions almost disappeared) to ≤ 0.5 (lesions strongly reduced).
3. **Stable disease:** Relative score > 0.5 (lesions weakly but significantly reduced) to 1.0 (lesions not reduced).
4. **Progressive disease:** New lesions on MIBG scan.

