12.5.1 Bone Marrow Involvement

Bone marrow obtained within 14 days prior to study enrollment with tumor cells seen on routine morphology (not by immunohistochemical staining only) of bilateral aspirate or biopsy on one bone marrow sample.

Bone Marrow responses are determined by H&E Staining of bilateral bone marrow biopsies and aspirates.

Complete Response: No tumor cells detectable by routine morphology on 2 consecutive bilateral bone marrow aspirates and biopsies performed at least 21 days apart. Normalization of urinary catecholamines or other tumor markers if elevated at study enrollment.

Progressive Disease: In patients who enroll with neuroblastoma in bone marrow by morphology have progressive disease if there is a doubling in the amount of tumor in the marrow AND a minimum of 25% tumor in bone marrow by morphology. (For example, a patient entering with 5% tumor in marrow by morphology must increase to $\geq 25\%$ tumor to have progressive disease; a patient entering with 30% tumor must increase to $> 60\%$).

In patients who enroll without evidence of neuroblastoma in bone marrow will be defined as progressive disease if tumor is detected in 2 consecutive bone marrow biopsies or aspirations done at least 21 days apart.

Stable Disease: Persistence of tumor in bone marrow that does not meet the criteria for either complete response or progressive disease.

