12.7 Best Response**12.7.1 Evaluation of Best Overall Response**

The best overall response is the best response recorded from the start of the treatment until disease progression/recurrence (taking as reference for progressive disease the smallest measurements recorded since the treatment started). The patient's best response assignment will depend on the achievement of both measurement and confirmation criteria.

Table 1: For Patients with Measurable Disease (i.e., Target Disease)

Target	Non-Target	New	Overall	Best Overall Response
--------	------------	-----	---------	-----------------------

THIS PROTOCOL IS FOR RESEARCH PURPOSES ONLY, SEE PAGE 1 FOR USAGE POLICY

Lesions	Lesions	Lesions	Response	when Confirmation is Required*
CR	CR	No	CR	≥ 28 days Confirmation
CR	Non-CR/Non-PD	No	PR	≥ 28 days Confirmation
CR	Not evaluated	No	PR	
PR	Non-CR/Non-PD/not evaluated	No	PR	
SD	Non-CR/Non-PD/not evaluated	No	SD	documented at least once ≥ 28 days from baseline
PD	Any	Yes or No	PD	no prior SD, PR or CR
Any	PD**	Yes or No	PD	
Any	Any	Yes	PD	

* See RECIST 1.1 manuscript for further details on what is evidence of a new lesion.
** In exceptional circumstances, unequivocal progression in non-target lesions may be accepted as disease progression.

Note: Patients with a global deterioration of health status requiring discontinuation of treatment without objective evidence of disease progression at that time should be reported as "symptomatic deterioration." Every effort should be made to document the objective progression even after discontinuation of treatment.

Table 2: For Patients with Non-Measurable Disease (i.e., Non-Target Disease)

Non-Target Lesions	New Lesions	Overall Response
CR	No	CR
Non-CR/non-PD	No	Non-CR/non-PD*
Not all evaluated	No	not evaluated
Unequivocal PD	Yes or No	PD
Any	Yes	PD

* 'Non-CR/non-PD' is preferred over 'stable disease' for non-target disease since SD is increasingly used as an endpoint for assessment of efficacy in some trials so to assign this category when no lesions can be measured is not advised

Table 3. Sequences of overall response assessments with corresponding best response.

1 st Assessment	2 nd Assessment	Best Response
Progression		Progressive disease
Stable, PR, CR	Progression	Progressive disease
Stable	Stable	Stable
Stable	PR, CR	Stable
Stable	Not done	Not RECIST classifiable
PR	PR	PR
PR	CR	PR
PR, CR	Not done	Not RECIST classifiable
CR	CR	CR

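### MIBG progression requires a new lesion and the Curie categories end at the pre-treatment score, so neuroblastoma that extends or regrows at known sites is scored stable or has no category

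*Protocol*

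**What the plan says.** Protocol 12.4.2 sets the treating institution's MIBG categories by counting lesions: "Stable disease: No change in MIBG scan in number of positive lesions" and "Progressive disease: Development of new MIBG positive lesions". Partial response there is the loss of at least one positive lesion while others remain.

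Protocol 12.4.3 sets the central reading, which it names as the basis for the efficacy endpoint, and asks the institution to apply the same scoring at the end of each course. Ten sectors are each scored 0 (no site), 1 (one site), 2 (more than one site) or 3 (over half the segment involved), and the scores are summed. The relative score is "calculated by dividing the absolute score at each time point by the corresponding pre-treatment absolute score". Partial response extends up to 0.5. Stable disease starts above 0.5 and is worded "lesions weakly but significantly reduced) to 1.0 (lesions not reduced". Progression is "New lesions on MIBG scan".

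Section 12.4.4 sends best response to Table 5 in 12.7. There, stable MIBG with no new CT/MRI lesion and no progression on bone scan or marrow gives overall stable disease. Section 12.7.1 judges best response by "taking as reference for progressive disease the smallest measurements recorded since the treatment started", and 12.7.2 uses the same reference for both durations.

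For marrow, 12.5.1 calls progression if "there is a doubling in the amount of tumor in the marrow AND a minimum of" 25% tumor. Its worked example requires a patient who enters at 30% to exceed 60%.

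**The concern.** A response scale should give every possible assessment one category, and worsening disease should not fall in the stable one. Here the central scale has no place for a score above baseline unless a new lesion is seen, and the institutional scale ignores extent. The fixed pre-treatment denominator also hides regrowth after a response until the score passes baseline, while 12.7.1 and 12.7.2 refer to the lowest value on treatment. The marrow rule has a ceiling of its own.

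At stake are best overall response, duration of response and duration of stable disease, which Protocol 11.6.7 summarises by dose level. Without a rule, a score above 1.0 has to be assigned case by case once results are known. The SAP does not mention MIBG and so gives no fallback. Sections 5.2 and 10.1(a) also depend on disease status as defined in Section 12.

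**Working it through.** The plan states no figure to reproduce. The check applies the protocol's own formula and categories.

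**Inputs (12.4.3).** Relative score = absolute score now / pre-treatment absolute score. CR: all uptake resolved. PR: up to 0.5. SD: above 0.5 to 1.0. PD: new lesion. If no new site appears, a segment at 0 stays at 0; one at 1 can go to 0, 1 or 3 (reaching 2 needs a second site); one at 2 or 3 can go to any value from 0 to 3.

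**1. Extension without a new lesion.**
- Single-site segments becoming massive: 3/1 = 3.0. Five such segments: 15/5 = 3.0. No central category; stable at the institution, because the count is unchanged.
- Segments going from 2 to 3: five of them give 15/10 = 1.5. No central category.
- Segments already at 3 cannot rise: 9/9 = 1.0, stable.
- With baseline (1,1), 5 of the 9 possible outcomes without a new site exceed 1.0: two at 1.5, two at 2.0 and one at 3.0. With baseline (2,2) it is 3 of 16. These count possible outcomes; they are not probabilities.
- The two readings can also disagree. From (1,1) to (0,3), one lesion resolves and the other becomes massive. The institution records PR; the central score is 3/2 = 1.5, with no category.

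**2. Regrowth where every segment stays positive.** Take five segments going from 3 to 1 and back to 3.
- Absolute scores: 15, then 5, then 15.
- Relative scores: 5/15 = 0.33 (PR), then 15/15 = 1.0 (SD).
- Change from the lowest score: 15/5 = 3, a three-fold rise.
- If only one of the five segments returns to 3, the score is 7 and 7/15 = 0.47. That is still PR, although 7/5 = 1.4 is a 40% rise from the lowest score.

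The lowest-value reference in 12.7.1 cannot operate here, because MIBG progression contains no score criterion.

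**3. Marrow (12.5.1).** Doubling from baseline b requires 2b to be at most 100%, so b at most 50%.
- Above 50% at entry the rule cannot be met. From 55% to 95% is 95/55 = 1.73 times, and the marrow is entered as Non-PD in Tables 4 and 5.
- From 30%, doubling is reached at 60%, but the example demands more than 60%. At exactly 50%, doubling is possible (100%), but under the example's strict inequality it is not.

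**The case against.** The strongest reply is that progression can be reached by other routes. Section 12.3.1 covers non-measurable disease seen by nuclear medicine, and 12.3.5 then accepts laboratory, clinical or radiographic progression. Tables 4 and 5 give overall PD from CT/MRI, bone scan or marrow. Section 10.1(a) includes clinical and marker evidence, and 10.1(f) leaves room for the physician's judgement. This narrows the problem, mainly to MIBG-only disease, but does not remove it. Neither 12.4 nor Tables 4 and 5 refers to 12.3.5, and 12.4.4 directs these patients to Table 5.

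Four stronger readings are tempting, and the documents do not support them:
- **That the SAP's ORR, DCR and PFS are inflated.** SAP 6.5.1 defines all three by RECIST 1.1, and 6.5.2 limits the best-response summary to patients assessable by RECIST 1.1. MIBG and marrow categories do not clearly enter.
- **That a five-fold regrowth such as 15 to 3 to 15 is always stable.** A score of 15 needs at least 15/3 = 5 segments, and a score of 3 occupies at most 3. At least two segments must clear and later return, which could be read as new lesions. The protocol does not say.
- **That each patient shifts a rate by 1/29 = 3.4 to 1/24 = 4.2 percentage points.** The SAP efficacy population is patients treated at the recommended dose, and response is reported by dose level, so 24 to 29 is not the denominator. After a confirmed response, regrowth changes duration and not the best response.
- **That marrow progression is impossible from 50% upward.** Under the doubling rule itself it is impossible only above 50%.

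**Conclusion.** The point holds in this limited form. As written, extension of known MIBG disease above baseline has no central category (relative scores above 1.0 and up to 3.0) and is stable by institutional lesion count when that count is unchanged. Regrowth of up to three-fold within segments that stayed positive can be scored stable, contrary to 12.7.1 and 12.7.2. Marrow progression is unreachable above 50% at entry, and its worked example does not match its rule.

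The effect is confined to a descriptive secondary aim: best response, duration of response and duration of stable disease under the protocol's criteria, in neuroblastoma patients and mainly those with MIBG-only disease. Their number is not given, so no overall size can be stated. Dose finding does not depend on these categories. The conclusion assumes that spread within a segment is not itself read as a new lesion, and that Table 5 governs these patients, as 12.4.4 says.

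**What to change.** For response reporting, reconcile 12.3.5, 12.4.2, 12.4.3, 12.7.1 and Tables 4 and 5:
- Give every relative score a category, including scores above 1.0 without a new lesion.
- Judge increases against the lowest earlier score, as 12.7.1 already states.
- State whether uptake returning at a cleared site counts as a new lesion.
- Make the marrow doubling rule and its worked example agree, and say how marrow is entered in Tables 4 and 5 when baseline exceeds 50%. Those tables have no row for marrow that is not evaluable, so adding such a label would mean changing them too.

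Any numeric margin should be chosen by the sponsor with the central reader, since the documents offer no basis for one, and recorded as a convention applied to the Curie scores already recorded. How 5.2 and 10.1(a) use these categories is for the sponsor to reconcile separately.

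The cost is wording and a documented convention; no added scans are needed. Central review under 8.3.2 covers only responders and patients stable for at least 3 cycles, so for other patients the convention rests on institutional scores. A few more assessments may be recorded as progression. Because Part A dose escalation is complete, the convention must be labelled as added late.

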12.4.4 Overall Best Response Assessment

Each patient will be classified according to his “best response” for the purposes of analysis of treatment effect. Best response is determined from the sequence of the overall response assessments as described in [Table 5 in Section 12.7](#).

12.5 **Response Criteria for Neuroblastoma Patients with Bone Marrow Involvement**

12.5.1 Bone Marrow Involvement

Bone marrow obtained within 14 days prior to study enrollment with tumor cells seen on routine morphology (not by immunohistochemical staining only) of bilateral aspirate or biopsy on one bone marrow sample.

Bone Marrow responses are determined by H&E Staining of bilateral bone marrow biopsies and aspirates.

Complete Response: No tumor cells detectable by routine morphology on 2 consecutive bilateral bone marrow aspirates and biopsies performed at least 21 days apart. Normalization of urinary catecholamines or other tumor markers if elevated at study enrollment.

Progressive Disease: In patients who enroll with neuroblastoma in bone marrow by morphology have progressive disease if there is a doubling in the amount of tumor in the marrow AND a minimum of 25% tumor in bone marrow by morphology. (For example, a patient entering with 5% tumor in marrow by morphology must increase to $\geq 25\%$ tumor to have progressive disease; a patient entering with 30% tumor must increase to $> 60\%$).

In patients who enroll without evidence of neuroblastoma in bone marrow will be defined as progressive disease if tumor is detected in 2 consecutive bone marrow biopsies or aspirations done at least 21 days apart.

Stable Disease: Persistence of tumor in bone marrow that does not meet the criteria for either complete response or progressive disease.

12.5.2 Overall Best Response Assessment

Each patient will be classified according to his “best response” for the purposes

THIS PROTOCOL IS FOR RESEARCH PURPOSES ONLY, SEE PAGE 1 FOR USAGE POLICY

of analysis of treatment effect. Best response is determined from the sequence of the overall response assessments as described in [Section 12.7](#).

12.6 Response Criteria for Patients with CNS Tumors

12.6.1 Measurable Disease

Any lesion that is at minimum 10 mm in one dimension on standard MRI or CT, for CNS tumors.

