At least a 20% increase in the sum of the diameters of target lesions, taking as reference the smallest sum on study (this includes the baseline sum if that is the smallest on study). In addition to the relative increase of 20%, the sum must also demonstrate an absolute increase of at least 5 mm. (Note: the appearance of one or more new lesions is also considered progressions). Note: in presence of SD or PR in target disease but unequivocal progression in non-target or non-measurable disease, the patient has PD if there is an overall level of substantial worsening in non-target disease such that the overall tumor burden has increased sufficiently to merit discontinuation of therapy

Stable Disease (SD):

Neither sufficient shrinkage to qualify for PR nor sufficient increase to qualify for PD, taking as reference the smallest sum diameters while on study

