12.6.3 Selection of Target and Non-Target Lesions

For most CNS tumors, only one lesion/mass is present and therefore is considered a “target” for measurement/follow up to assess for tumor progression/response. If multiple measurable lesions are present, up to 5 should be selected as “target” lesions. Target lesions should be selected on the basis of size and suitability for accurate repeated measurements. All other lesions will be followed as non-target lesions. The lower size limit of the target lesion(s) should be at least twice the thickness of the slices showing the tumor to decrease the partial volume effect (e.g., 8 mm lesion for a 4 mm slice).

Any change in size of non-target lesions should be noted, though does not need to be measured.

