12.6.4 Response Criteria for Target Lesions

Response criteria are assessed based on the product of the longest diameter and its longest perpendicular diameter. Development of new disease or progression in any established lesions is considered progressive disease, regardless of response in other lesions – e.g., when multiple lesions show opposite responses, the progressive disease takes precedence. Response Criteria for target lesions:

- **Complete Response (CR):** Disappearance of all target lesions.
- **Partial response (PR):** $\geq 50\%$ decrease in the sum of the products of the two perpendicular diameters of all target lesions (up to 5), taking as reference the initial baseline measurements.
- **Stable Disease (SD):** Neither sufficient decrease in the sum of the products of the two perpendicular diameters of all target lesions to qualify for PR, nor sufficient increase in a single target lesion to qualify for PD.
- **Progressive Disease (PD):** 25% or more increase in the sum of the products of the perpendicular diameters of the target lesions, taking as reference the smallest sum of the products observed since the start of treatment, or the appearance of one or more new lesions.

12.6.5 Response Criteria for Non-Target Lesions:

- **Complete Response (CR):** Disappearance of all non-target lesions.
- **Incomplete Response/Stable Disease (IR/SD):** The persistence of one or more non-target lesions.
- **Progressive Disease (PD):** The appearance of one or more new lesions and/or unequivocal progression of existing non-target lesions.

12.6.6 Response criteria for tumor markers (if available):

Tumor markers will be classified simply as being at normal levels or at abnormally high levels.

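### CNS target lesions have two inconsistent lower size limits (12.6.1 and 12.6.3) and no minimum second diameter, so for lesions near the floor about 1 mm of error in each diameter can be called progression

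*Protocol*

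**What the plan says.** Four parts of Protocol 12.6 bear on this.

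- **12.6.1, measurable disease:** "Any lesion that is at minimum 10 mm in one dimension on standard MRI or CT, for CNS tumors". The floor applies to one dimension.
- **12.6.3, choice of targets:** "The lower size limit of the target lesion(s) should be at least twice the thickness of the slices showing the tumor", with the illustration "e.g., 8 mm lesion for a 4 mm slice". It does not say which dimension this covers or whether it adds to the 10 mm floor. Where there are several lesions, "If multiple measurable lesions are present, up to 5 should be selected as" targets. A single lesion is simply treated as the target.
- **12.6.4, scoring:** "Response criteria are assessed based on the product of the longest diameter and its longest perpendicular diameter". PD is a "25% or more increase in the sum of the products of the perpendicular diameters of the target lesions", measured from the smallest sum since treatment began. No minimum absolute increase is required.
- **12.6.2, evaluable disease:** this category requires that no lesion can be measured accurately in even one dimension.

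For non-CNS solid tumors, Protocol 12.2.4.1 does carry an absolute floor on progression: "the sum must also demonstrate an absolute increase of at least 5 mm".

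Protocol 12.7, Table 3, assigns a best response of progressive disease when stable disease, PR or CR at the first assessment is followed by progression at the second. Section 10.1(a) makes radiographic progression a criterion for removal from protocol therapy.

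**The concern.** There are two linked faults. First, an 8 mm lesion on 4 mm slices is acceptable as a target under 12.6.3 but falls short of measurable disease under 12.6.1. Sites can apply either rule, and the choice decides whether the lesion is scored by its diameters or not.

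Second, the entry rule and the response measure do not match. A lesion enters on one diameter but is scored on the product of two. A thin lesion such as 10 x 5 mm qualifies, and a small absolute error in its short diameter is a large percentage error in the product. Without an absolute-increase floor, measurement noise alone can pass the 25% threshold.

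Little downstream would catch such a false call. Section 12.7 lists no confirmation step for progression. Central review under 8.3.2 covers responders and patients stable for at least 3 cycles, not early progressors. Section 12.6.4 lets progression in any established lesion take precedence, so having several targets does not reliably protect a patient. Part B plans only up to 6 evaluable patients (Protocol 11.1).

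**Working it through.** **1. The plan's own figure.** Lower limit = 2 x slice thickness. For a 4 mm slice, 2 x 4 = 8 mm, as 12.6.3 states. Any slice thinner than 5 mm gives a limit below 10 mm (3 mm gives 6 mm).

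**2. Can the two limits be read together?** If a target must be at least 10 mm and at least twice the slice thickness, then on 4 mm slices the operative limit is 10 mm and the 8 mm example can never apply. If 12.6.3 stands alone, 8 mm is accepted and 12.6.1 is contradicted. On either reading one sentence is wrong.

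**3. Error of 1 mm in each diameter, no true change.** Relative change = (a + 1)(b + 1)/(ab) - 1, with PD at 25% or more. The error e needed in both diameters to reach PD solves (a + e)(b + e) = 1.25ab, so e = [-(a + b) + sqrt((a + b)^2 + ab)]/2.

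| True size (mm) | Read as | Products | Change | Call | e for PD (mm) |
|---|---|---|---|---|---|
| 10 x 5 | 11 x 6 | 50 to 66 | +32.0% | PD | 0.79 |
| 10 x 7 | 11 x 8 | 70 to 88 | +25.7% | PD | 0.97 |
| 8 x 8 | 9 x 9 | 64 to 81 | +26.6% | PD | 0.94 |
| 10 x 10 | 11 x 11 | 100 to 121 | +21.0% | SD | 1.18 |
| 20 x 20 | 21 x 21 | 400 to 441 | +10.3% | SD | 2.36 |

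The 10 x 5 and 10 x 7 rows satisfy 12.6.1 as written and do not depend on the 8 mm example.

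**4. How often noise alone gives PD.** The documents give no measurement error, so the SD here is an assumption, shown as a range. Each diameter has independent normal error with SD 0.5 or 1 mm at baseline and at two follow-up scans, the single lesion does not change, and PD is called if a product is at least 1.25 times the smallest earlier product. There were 400,000 simulated patients per row.

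| True size (mm) | SD 0.5, first scan | SD 0.5, by second scan | SD 1, first scan | SD 1, by second scan |
|---|---|---|---|---|
| 10 x 5 | 8% | 19% | 24% | 50% |
| 8 x 8 | 3.8% | 9.7% | 19% | 41% |
| 10 x 10 | 1.3% | 3.6% | 13% | 30% |
| 20 x 20 | about 0% | about 0% | 1.3% | 3.6% |

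**5. Which results are touched.** Protocol best response (12.7, Table 3) and removal under 10.1(a) follow directly from a 12.6.4 call. SAP 6.5.1 defines ORR, DCR and PFS by RECIST 1.1 and does not cite 12.6, so the calculation does not carry over to them.

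**The case against.** The best defence is that the two limits are cumulative. Section 12.6.3 draws multiple targets from lesions that are already measurable, the twice-slice rule is phrased as a minimum aimed at partial-volume effects, and 8 mm only illustrates a ratio. This is a fair reading, and it shrinks the first fault to a clarification. It does not rescue the example, and it leaves the missing second-diameter minimum untouched.

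It can also be said that 12.6.3 already asks for lesions suited to accurate repeated measurement, which disfavours thin ones. That helps only where there is a choice, and the section itself says most CNS tumors present a single lesion.

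Three stronger inferences are tempting, and the documents do not support them:

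- **That 1 mm of error generally turns stable disease into PD in Part B.** It does so only near the floor. At 10 x 10 mm it does not, and at 20 mm or more it is far from doing so. The documents give no CNS lesion sizes, so the frequency is unknown.
- **That one false PD moves DCR by one patient in 6, or shifts PFS.** The SAP measures these by RECIST 1.1, counts all treated patients in the denominator, and reports DCR by dose level rather than for Part B alone (6.5.1, 6.5.2). SAP 6.5.2 also takes the best response recorded before progression, so stable disease at scan 1 would survive a false PD at scan 2. Only Protocol Table 3 overrides it.
- **That the primary conclusions are at risk.** Part B's primary question is tolerability, response is secondary and descriptive (Protocol 1.2, 11.5), and the first on-study tumor evaluation is at the end of cycle 1, as the DLT window closes.

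**Conclusion.** The concern holds within limits. The lower size limits in 12.6.1 and 12.6.3 are inconsistent and need reconciling, and the absence of a second-diameter minimum beside a product-based 25% threshold leaves small or thin lesions exposed to false progression.

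The size depends on the lesion and on an assumed error SD of 0.5 to 1 mm per diameter, independent between diameters and scans. By the second scan, false PD is about 19% to 50% for 10 x 5 mm, 3.6% to 30% for 10 x 10 mm and 0% to 4% for 20 x 20 mm.

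What is at stake is a wrong protocol best response and removal from therapy for individual patients in a small descriptive cohort. DLT and RP2D conclusions are unaffected, and no effect on DCR or PFS is claimed. The change is worth making because it is cheap, but it is not critical.

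**What to change.** Reconcile 12.6.1 and 12.6.3 into one rule: a CNS target lesion must measure at least 10 mm, and at least twice the slice thickness, in both perpendicular diameters. Delete the 8 mm example.

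Amend 12.6.2 at the same time, so that lesions below this limit count as evaluable, are followed as non-target and are scored under 12.6.5. Without that, a lesion of, say, 30 x 9 mm would be neither measurable (short diameter under 10 mm) nor evaluable (it can be measured accurately in one dimension).

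The cost is protocol wording. Section 4.1.3 admits measurable or evaluable disease, so eligibility need not change. It points to 12.2 and 12.3 for the definitions, not to 12.6, so the cross-reference should be checked in the same edit.

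There are two downsides. A patient with only thin or small lesions can no longer score a PR. The rule also reduces false PD without removing it. Comparing 10 x 5 mm with the smallest square lesion still allowed on slices up to 5 mm, 10 x 10 mm, the risk by the second scan falls from about 19% to 3.6% at SD 0.5 mm, but only from about 50% to 30% at SD 1 mm. An absolute-increase floor, which 12.2.4.1 already has for non-CNS tumors, would add protection if larger measurement error is expected.
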